- e Local Tolerability Assessments: the Investigator local tolerability assessment of skin irritation (Berger and Bowman skin irritation score) should be performed prior to the investigational product application at Day 0, Weeks 4 and 8. **Note for investigator tolerability assessments: reactions at the site of product application, which may occur post-Baseline, should be differentiated from the preexisting inflammation associated with the subject's Psoriasis.** Subjects will perform the local tolerability 10-15 minutes post-IP application at Day 0 and Week 4, and recall assessment at Week 8 for the subject's '0-3' burning/stinging assessment.
- f Adolescents and adults will complete the C-SSRS. Adults will complete the PHQ-8. Adolescents will complete a modified version of the PHQ-A (PHQ-9 modified for Adolescents).
- g At selected sites, medical photography will be obtained for target lesions. All efforts will be made to de-identify the subjects. Subjects who are unwilling to participate in the medical photography will be allowed to opt out of this procedure.
- h A pregnancy test will be administered to all females of child-bearing potential. A serum pregnancy test will be performed at the Screening visit only. A urine pregnancy test will be performed at Day 0, Week 4, and Week 8. A negative result is required for continued participation in the study, and results must be available prior to dispensing of the IP at each visit.
- i PK draws will be collected at Days 0, Weeks 4 and 8 pre-dose (within 1 hour) for all subjects. Serial PK will be obtained in a subset of approximately 15 subjects on Days 0 and 28 at 1, 2, 4, 6 (all  $\pm$  20 min), and 24 hours ( $\pm$  2 hours) post-dose
- j Subjects to apply assigned IP in clinic at Day 0, Weeks 2 and 4.
- k Kits will be dispensed based on %BSA affected. See IP Handling Manual for details.
- l The entire kit should be weighed and recorded at every visit. See IP Handling Manual for details.
- m Compliance calculation is described in the IP Handling Manual
- n Any emergent AEs will be followed in the clinic for up to one month at the Investigator's discretion until resolved or otherwise judged as clinically stable.

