#### 5.1.9 Local Tolerability Assessments

The Investigator Local Tolerability Assessment will be an overall assessment of local tolerability and performed as follows:

Baseline, Weeks 4, and 8

Application site reactions will be graded at the timepoints outlined in the Schedule of Visits and Assessments ([Section 1.3](#)). Irritation reactions are graded using the scale detailed in the following section ([Berger 1982](#)). **Reactions at the site of product application, which may occur post-Baseline, should be differentiated from the preexisting inflammation associated with the subject's psoriasis.**

The investigator assessments will be conducted by the investigator prior to IP application in the clinic for applicable visits.

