#### Other Effects

A = slight glazed appearance

B = marked glazing

C = glazing with peeling and cracking

D = glazing with fissures

E = film of dried serous exudates

F = small petechial erosions and/or scabs

G = no other effects

The Subject Local Tolerability Assessment will be an overall assessment of local tolerability and performed as follows:

Baseline, Weeks 4, and 8

The assessment will be administered by the site 10 to 15 minutes after IP application in the clinic at Baseline and Week 4, and a recall assessment at Week 8.

Grade	Sensation Following Drug Application
0 (none)	No sensation
1 (mild)	Slight warm, tingling sensation; not really bothersome
2 (moderate)	Definite warm, tingling sensation that is somewhat bothersome
3 (severe)	Hot, tingling/stinging sensation that has caused definite discomfort

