9.2. Local Tolerability Assessments

The investigator's assessment of the application site reaction will be summarized by study visit using both categorical methods (number and percentage of subjects with each score) as well as continuous methods (e.g., mean, median). Categorical summaries will be provided for dermal response as well as other effects. No inferential statistical tests will be performed.

The subject's assessment of the application site reaction will be summarized similarly.

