 Reference Listing: 16.2.9.7

Table 14.3.6.2.1
Summary of Investigator Local Tolerability Assessment (Dermal Response) by Study Visit
Safety Population

(Same shell as Table 14.3.5.1.1; Reference Listing: 16.2.9.1; Repeat for Week 4, Week 8; Add this line at the end in note footnote – “Lower scores indicate no evidence of irritation while higher scores indicate worsening reaction. These assessments should be done prior to the IP application in the study site. Subjects not meeting this condition on baseline visit are completely removed from the table summary.”)

Table 14.3.6.2.2
Summary of Investigator Local Tolerability Assessment (Dermal Response) by Study Visit
Categorical Results
Safety Population

Study Visit Category	Roflumilast Foam 0.3% (N=XX)	Vehicle (N=XX)	Overall (N=XX)
Baseline			
0 = No evidence of irritation	XX (XX.X%)	XX (XX.X%)	XX (XX.X%)
1 = Minimal erythema	XX (XX.X%)	XX (XX.X%)	XX (XX.X%)
2 = Definite erythema	XX (XX.X%)	XX (XX.X%)	XX (XX.X%)
3 = Erythema and papules	XX (XX.X%)	XX (XX.X%)	XX (XX.X%)
4 = Definite edema	XX (XX.X%)	XX (XX.X%)	XX (XX.X%)
5 = Erythema, edema and papules	XX (XX.X%)	XX (XX.X%)	XX (XX.X%)
6 = Vesicular eruption	XX (XX.X%)	XX (XX.X%)	XX (XX.X%)
7 = Strong reaction spreading beyond application site			
Week 4			
0 = No evidence of irritation	XX (XX.X%)	XX (XX.X%)	XX (XX.X%)
1 = Minimal erythema	XX (XX.X%)	XX (XX.X%)	XX (XX.X%)
2 = Definite erythema	XX (XX.X%)	XX (XX.X%)	XX (XX.X%)
3 = Erythema and papules	XX (XX.X%)	XX (XX.X%)	XX (XX.X%)
4 = Definite edema	XX (XX.X%)	XX (XX.X%)	XX (XX.X%)
5 = Erythema, edema and papules	XX (XX.X%)	XX (XX.X%)	XX (XX.X%)
6 = Vesicular eruption	XX (XX.X%)	XX (XX.X%)	XX (XX.X%)
7 = Strong reaction spreading beyond application site			

Repeat for Week 8

Abbreviation: IP = investigational product.

Note: Percentages are n/Number of subjects in the Safety Population within treatment received and overall*100. Baseline is the last non-missing measurement taken before the first application of study drug. These assessments should be done prior to the IP application in the study site. Subjects not meeting this condition on baseline visit are completely removed from the table summary. Reference Listing: 16.2.9.1

Table 14.3.6.2.3
Summary of Investigator Local Tolerability Assessment (Other Effects) by Study Visit
Categorical Results
Safety Population

Study Visit Category	Roflumilast Foam 0.3% (N=XX)	Vehicle (N=XX)	Overall (N=XX)
Baseline			

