A = Slight glazed appearance	XX (XX.X%)	XX (XX.X%)	XX (XX.X%)
B = Marked glazing	XX (XX.X%)	XX (XX.X%)	XX (XX.X%)
C = Glazing with peeling and cracking	XX (XX.X%)	XX (XX.X%)	XX (XX.X%)
D = Glazing with fissures	XX (XX.X%)	XX (XX.X%)	XX (XX.X%)
E = Film of dried serous exudates	XX (XX.X%)	XX (XX.X%)	XX (XX.X%)
F = Small petechial erosions and/or scabs	XX (XX.X%)	XX (XX.X%)	XX (XX.X%)
G = No other effects	XX (XX.X%)	XX (XX.X%)	XX (XX.X%)
Week 4			
A = Slight glazed appearance	XX (XX.X%)	XX (XX.X%)	XX (XX.X%)
B = Marked glazing	XX (XX.X%)	XX (XX.X%)	XX (XX.X%)
C = Glazing with peeling and cracking	XX (XX.X%)	XX (XX.X%)	XX (XX.X%)
D = Glazing with fissures	XX (XX.X%)	XX (XX.X%)	XX (XX.X%)
E = Film of dried serous exudates	XX (XX.X%)	XX (XX.X%)	XX (XX.X%)
F = Small petechial erosions and/or scabs	XX (XX.X%)	XX (XX.X%)	XX (XX.X%)
G = No other effects	XX (XX.X%)	XX (XX.X%)	XX (XX.X%)

Repeat for Week 8

Abbreviation: IP = investigational product.

Note: Percentages are n/Number of subjects in the Safety Population within treatment received and overall*100. Baseline is the last non-missing measurement taken before the first application of study drug. These assessments should be done 10 - 15 minutes after the application of IP in the study site. Subjects not meeting this condition on baseline visit are completely removed from the table summary.

Reference Listing: 16.2.9.1

Table 14.3.6.3.1
Summary of Subject Local Tolerability Assessment by Study Visit
Safety Population

(Same shell as Table 14.3.5.1.1; Reference Listing: 16.2.9.2; Repeat for Week 4, Week 8; add "IP = investigational product" to abbreviations; Add this line at the end in note footnote – "Lower scores indicate no sensation while higher scores indicate worsening/severe sensation. These assessments should be done 10 - 15 minutes after the application of IP in the study site. Subjects not meeting this condition on baseline visit are completely removed from the table summary." Change baseline definition to "Baseline for subject local tolerability assessment is the last non-missing measurement taken on the day of first application of study drug.")

Table 14.3.6.3.2
Summary of Subject Local Tolerability Assessment by Study Visit
Categorical Results
Safety Population

Study Visit Category	Roflumilast Foam 0.3% (N=XX)	Vehicle (N=XX)	Overall (N=XX)
Baseline			
0 = None (no sensation)	XX (XX.X%)	XX (XX.X%)	XX (XX.X%)
1 = Mild (slight warm, tingling sensation)	XX (XX.X%)	XX (XX.X%)	XX (XX.X%)

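### The shell for the investigator Other Effects tolerability table carries the subject-rated timing condition; read literally, it removes every subject whose baseline assessment followed the protocol

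*SAP*

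**What the plan says.** Protocol Section 1.3, footnote e, states that the investigator's skin irritation assessment "should be performed prior to the investigational product application at Day 0, Weeks 4 and 8". Protocol Section 5.1.9 agrees: "The investigator assessments will be conducted by the investigator prior to IP application in the clinic for applicable visits". That assessment has two parts, a Dermal Response grade (0 to 7) and an Other Effects code (A to G). The subject's 0 to 3 sensation score is a separate assessment: "The assessment will be administered by the site 10 to 15 minutes after IP application in the clinic at Baseline and Week 4", with recall at Week 8.

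SAP Section 9.2 treats both investigator parts as one assessment: "Categorical summaries will be provided for dermal response as well as other effects". In SAP Section 14.2, the shells for Dermal Response (Tables 14.3.6.2.1 and 14.3.6.2.2) carry the condition "These assessments should be done prior to the IP application in the study site".

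The shell for Other Effects (Table 14.3.6.2.3) carries a different one: "These assessments should be done 10 - 15 minutes after the application of IP in the study site". The next sentence makes it an inclusion rule: "Subjects not meeting this condition on baseline visit are completely removed from the table summary". The same footnote defines baseline in pre-application terms: "Baseline is the last non-missing measurement taken before the first application of study drug".

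**The concern.** The removal sentence is an operative instruction to the programmer. In the Dermal Response shells it removes subjects who were assessed at the wrong time. In the Other Effects shell the same sentence follows the opposite timing condition, so it removes subjects who were assessed at the right time.

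Two things are at stake. First, local tolerability is a listed safety endpoint (SAP Section 2.2.1), and Table 14.3.6.2.3 is the only planned summary of glazing, fissures, exudate and erosions as rated by the investigator. Second, two halves of one assessment would be reported on different sets of subjects. Even if the programmer applied the intended rule, the printed footnote would misstate in the study report when the assessment was made.

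**Working it through.** The plan gives no figure to reproduce. The check is a comparison of texts, followed by the logical consequence of the rule.

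**Step 1. Timing of the investigator assessment, by source.**

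| Source | Timing relative to application |
|---|---|
| Protocol 1.3, footnote e | before |
| Protocol 5.1.9 | before |
| SAP Table 1, footnote e | before |
| SAP shells 14.3.6.2.1 and 14.3.6.2.2 (Dermal Response) | before |
| SAP Listing 16.2.9.1 (the listing that Table 14.3.6.2.3 names as its source) | before |
| SAP shell 14.3.6.2.3 (Other Effects) | 10 to 15 minutes after |

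The last row is the only exception.

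**Step 2. Where the odd sentence belongs.** The timing and removal sentences in 14.3.6.2.3 are the same as those in the subject-rated shells 14.3.6.3.1 and 14.3.6.3.2, where the post-application timing is correct. SAP Section 10, which lists changes from the planned analysis, mentions no change in investigator timing.

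**Step 3. One record, two rules.** Listing 16.2.9.1 shows Dermal Response and Other Effects side by side under one assessment date and time. A Day 0 record made before application passes the condition in 14.3.6.2.2 and fails the one in 14.3.6.2.3. Failure at baseline removes the subject from the whole table, so Baseline, Week 4 and Week 8 are all lost.

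**Step 4. The footnote against itself.** A record used as baseline must precede first application, yet the condition requires it to follow application by 10 to 15 minutes. No single record can do both. The subject-rated shells avoid this by redefining baseline as a measurement on the day of first application. SAP Section 6.1.1 makes that allowance for subject local tolerability only.

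**Step 5. The footnote against the SAP text.** SAP Section 6.1.1 excludes tolerability records that were not done per protocol. That rule keeps a pre-application investigator record; the shell discards it.

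**Step 6. Size.** Let N be about 300 (the planned total, SAP Section 3.2) and let c be the fraction of subjects whose only Day 0 investigator assessment was made before application. The number kept is at most N × (1 − c). With full compliance, c = 1 and 300 × (1 − 1) = 0. For c below 1 the expression is only an upper bound, because an assessment outside the 10 to 15 minute window also fails.

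**The case against.** The best reply is that the SAP already contains the right rule. Section 6.1.1 keeps records done per protocol, Table 1 and Listing 16.2.9.1 give the correct timing, and Section 9.2 treats the two parts as one assessment. On this view a single shell footnote contains a copying error, and an empty table next to full ones would be noticed at once. The table is descriptive, with no inferential test. Every subject's Other Effects code still appears in the listing, and application site reactions that need intervention, suspension or discontinuation are recorded as adverse events (Protocol Section 5.7.1).

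Most of this stands, and it limits the scope of the point. It does not remove the contradiction: the SAP still gives two opposing inclusion rules for one table.

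Two stronger readings are tempting and should not be drawn.

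- A reader might infer that the table would show only the subjects assessed at the wrong time. The documents do not support this. The condition is tested at the baseline visit only, so later mistiming is irrelevant. It requires 10 to 15 minutes, so a rating outside that window fails too. A subject assessed only after application has no baseline under Section 6.1.1, and off-protocol records are excluded there as well.
- A reader might infer a falsely reassuring table with adverse codes near 0%. The shell takes percentages over the Safety Population and does not say whether removed subjects leave the denominator. But with all subjects removed, code G (no other effects) would also be near 0%, so the table would look empty rather than clean.

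**Conclusion.** The point holds as an internal contradiction in one SAP table shell. The post-application condition in Table 14.3.6.2.3 disagrees with every other statement of investigator timing in both documents, with the exclusion rule in SAP Section 6.1.1, and with the baseline definition in its own footnote. Applied literally, it removes at all visits every subject whose only Day 0 investigator assessment was made per protocol.

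The result of 0 of about 300 rests on two assumptions: the footnote is programmed as written, and all subjects were assessed on time. A programmer who followed Section 6.1.1 instead would produce a correct table under an incorrect footnote. That the sentence was carried over from the subject-rated shells is an inference from its identical wording.

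The damage is confined to one descriptive table. It should be corrected because the rule is wrong as written and the table summarises part of a listed safety endpoint. It does not put the tolerability assessment as a whole in doubt.

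**What to change.** In the footnote of Table 14.3.6.2.3, replace the timing sentence with the one used in the Dermal Response shells: "These assessments should be done prior to the IP application in the study site". The removal sentence can then stay, since it would act on mistimed assessments as it does in Tables 14.3.6.2.1 and 14.3.6.2.2.

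At the same time, check the cross-reference in SAP Section 6.1.1. It points to protocol Section 5.1.8 for tolerability assessments, but in the supplied protocol 5.1.8 is the C-SSRS and local tolerability is 5.1.9. The SAP is written against Amendment Version 1.0, whereas the supplied protocol includes the changes of Amendment 2, so the numbering may have differed. That is an assumption to verify.

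The cost is one footnote sentence, one programming condition and possibly one section number. No study procedure changes.

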14.3. Planned Listing Shells

Listing 16.2.1.1
Subject Disposition
All Subjects

Subject ID	Randomized Treatment	Complete Study? [1] eCRF Derived	Did Subject Complete Study? [1] Derived	Date of Completion/ Early Termination (Study Day)	Date of Last Study Visit (Study Day)	Reason for Early Termination [2]	Cause of Death/ Date of Death	Early Termination Due to COVID-19 Disruption
XXXXXX	XXXXXX	Yes	Yes	DDMMYYYY (XX)	DDMMYYYY (XX)			
XXXXXX	XXXXXX	Yes	Yes	DDMMYYYY (XX)	DDMMYYYY (XX)			
XXXXXX	XXXXXX	Yes	Yes	DDMMYYYY (XX)	DDMMYYYY (XX)			
XXXXXX	XXXXXX	No	Yes	DDMMYYYY (XX)	DDMMYYYY (X)	XXXXXXXXXX: XXXXXXXXXX		
XXXXXX	XXXXXX	No	Yes	DDMMYYYY (XX)	DDMMYYYY (XX)	XXXXXX	XXXXXX/ DDMMYYYY	XXX

Abbreviations: COVID-19 = novel coronavirus disease-19; eCRF = electronic case report form.

Note: Study day is calculated relative to the date of first application of study drug.

[1] The derived completion status is based on a subject completing the Week 8 visit; this is what is used in the subject disposition summary. The eCRF completion status is based on what was recorded in the eCRF.

[2] Based on the eCRF.

Programming Note: If reason for early termination is Other, concatenate the specify text as follows: "Other: XXXXXXXXXXXX"; if reason for early termination is lost to follow-up, concatenate with date of last contact as follows: "Lost to follow-up; date of last contact: DDMMYYYY".

Listing 16.2.1.2
 Subject Visits
 All Subjects

Subject ID	Treatment Received	Was Visit Performed?	Visit	Visit Date (Study Day)	If Visit not Performed, COVID-19 Disruption Contributed to Missed Visit
XXXXXX	XXXXXX	Yes	XXXXXXXXXX	DDMMYYYY (XX)	
		Yes	XXXXXXXXXX	DDMMYYYY (XX)	
		Yes	XXXXXXXXXXXX	DDMMYYYY (XX)	
		No	XXXXXXXXXX		Yes
XXXXXX	XXXXXX	Yes	XXXXXXXXXX	DDMMYYYY (XX)	
		Yes	XXXXXXXXXX	DDMMYYYY (XX)	

Abbreviation: COVID-19 = novel coronavirus disease-19.

Note: Study day is calculated relative to the date of first application of study drug.

Listing 16.2.2.1
Inclusion and Exclusion Criteria
All Subjects

Subject ID	Was Subject Rescreened?	Subject Screen Failed due to COVID-19 Disruption	Randomized Treatment	Date/Time (Study Day) of:			All Inclusion Criteria Met? [1]	Any Exclusion Criteria Met? [2]
				Screening	Informed Consent	If Adolescent, Date of Written Assent		
XXXXXX	XX		XXXXXX	DDMMYYYY (-X)	DDMMYYYYY/hh:m m (-X)	Yes	No	
XXXXXX	XX	XX		DDMMYYYY	DDMMYYYY	No: 05, 13	No	
XXXXXX	XX	XX		DDMMYYYY	DDMMYYYYY/hh:m m	No: 02	No	
XXXXXX	XXX		XXXXXX	DDMMYYYY (-X)	DDMMYYYY	Yes	Yes: 02	
XXXXXX	XX		XXXXXX	DDMMYYYY (-X)	DDMMYYYY	Yes	No	
XXXXXX	XX		XXXXXX	DDMMYYYY (-X)	DDMMYYYY	Yes	No	

Abbreviation: COVID-19 = novel coronavirus disease-19.

Note: Study day is calculated relative to the date of first application of study drug. If a subject is a rescreen, the latest date of screening and informed consent are presented. [1] 02 = Males and females ages 12 years and older (inclusive) at the time of consent or assent (for adolescents); 05 = A Psoriasis Scalp Severity Index (PSSI) score of at least 6 at Baseline; 13 = Subjects are considered reliable and capable of adhering to the Protocol and visit schedule according to the Investigator judgment. [2] 02 = Planned excessive exposure of treated area(s) to either natural or artificial sunlight, tanning bed or other LED.

Programming note: If more than 1 inclusion or exclusion criterion number exists, concatenate with a comma as shown above. Decode any relevant criteria in the footnotes as shown in the example. If no criteria are present for a column, remove the [1] and/or [2] from the column header. Time is only collected for informed consent. If time is missing, display as shown in the shell. If subject rescreens, populate the latest date of screening and informed consent.

Listing 16.2.2.2
 Protocol Deviations
 All Subjects

Subject ID	Treatment Received	Date of Protocol Violation Collection (Study Day)	Event Type	Violation Level	Description	COVID-19 Related	COVID-19 Infection	Action/Resolution
XXXXXX	XXXXXX	DDMONYYYY (XX)	XXXXXXXXXXXXXXXXXX	Minor	XXXXXXX			
		DDMONYYYY (XX)	XXXXXXXXXXXXXXXXXX	Major	XXXXXXXXXXXXXXXXXXXX			
XXXXXX	XXXXXX	DDMONYYYY (XX)	XXXXXXXXXXXXXXXXXX	XXXXX	XXXXXXXXXXXXXXXXXXXX	XXX	XXX	
		DDMONYYYY (XX)	XXXXXXXXXXXXXXXXXX	XXXXX	XXXXXXXXXXXX			
XXXXXX	XXXXXX	DDMONYYYY (XX)	XXXXXXXXXXXXXXXXXX	XXXXX	XXXXXXXXXXXXXXXXXXXX	XX	XX	

Abbreviation: COVID-19 = novel coronavirus disease-19.

Note: Study day is calculated relative to the date of first application of study drug.

Programming note: the structure of this listing may change depending on the information in the protocol deviations file.

Listing 16.2.3.1
 Subject Randomization
 All Subjects

Subject ID	Treatment Received	Randomized Treatment	Randomization		
			Date/Time	Number	Stratification ID
XXXXXX	XXXXXX	XXXXX	DDMMYY/ hh:mm	XXXX	XXXX
XXXXXX	XXXXXX	XXXXX	DDMMYY/ hh:mm	XXXX	XXXX
XXXXXX					

Listing 16.2.3.2
Analysis Populations
All Subjects

Subject ID	Treatment Received	Safety [1]	ITT [2]	mITT [3]	SPRU4-ITT [4]	SPRU4-mITT [4]	PRU4-ITT [5]	PRU4-mITT [5]	PK [6]	Primary Reason(s) for Exclusion [7]
XXXXXX	XXXXXX	Yes	Yes	No	Yes	XXX	XXX	XXX	XXX	Subject missed Week 8 disease assessment specifically due to COVID-19 disruptions.
XXXXXX	XXXXXX	Yes	Yes	Yes	Yes	XXX	XXX	XXX	XXX	
XXXXXX	XXXXXX	No	Yes	No	No	XXX	XXX	XXX	XXX	Subject did not receive at least 1 dose of IP.

Abbreviations: COVID-19 = novel coronavirus disease-19; ITT = intent-to-treat; IP = investigational product; mITT = modified intent-to-treat; NA = not applicable; PK = pharmacokinetic; PRU4 = Subjects with WI-NRS Pruritus Score ≥ 4 at Baseline; SI-NRS = Scalp Itch – Numeric Rating Scale; SPRU4 = Subjects with SI-NRS Pruritus Score ≥ 4 at Baseline; WI-NRS = Worst Itch – Numeric Rating Scale.

[1] The Safety Population includes all subjects who are enrolled and received at least 1 confirmed dose of IP.

[2] The ITT Population includes all subjects who are randomized.

[3] The mITT population includes all randomized subjects with the exception of subjects who missed the Week 8 S-IGA assessment specifically due to COVID-19 disruptions.

[4] The SPRU4-ITT and SPRU4-mITT populations are subsets of the ITT and mITT populations, respectively, and include subjects with SI-NRS pruritus score ≥ 4 at Baseline. These populations will be used for the analyses of achievement of a 4-point reduction in SI-NRS pruritus score as compared to Baseline.

[5] The PRU4-ITT and PRU4-mITT populations are subsets of the ITT and mITT populations, respectively, and include subjects with WI-NRS pruritus score ≥ 4 at Baseline. These populations will be used for the analyses of achievement of a 4-point reduction in WI-NRS pruritus score as compared to Baseline.

[6] The PK population includes all subjects receiving the active drug with sufficient plasma concentrations of roflumilast to define a profile, as determined by the pharmacokineticist.

[7] Applies to the Safety, ITT, and mITT populations only.

Listing 16.2.4.1.1
 Subject Demographics
 All Subjects

Subject ID	Treatment Received	Sex	Child-Bearing Potential? If Yes, Specify Contraception	Year of Birth	Age (years) [1]	Ethnicity	Race	Photography Consent Obtained/ Date of Consent	PK Consent Obtained/ Date of Consent
XXXXXX	XXXXXX	XXXX	No	YYYY	XX	XXXXXXXX	XXXXXXXX	Yes/ DDDMMYYYY	Yes/ DDDMMYYYY
XXXXXX	XXXXXX	XXXXXX	No	YYYY	XX	XXXXXXXX	XXXXXX	Yes/ DDDMMYYYY	Yes/ DDDMMYYYY
XXXXXX	XXXXXX	XXXX		YYYY	XX	XXXXXXXX	XXXXXX	No	No
XXXXXX	XXXXXX	XXXX		YYYY	XX	XXXXXXXX	XXXXXX	Yes/ DDDMMYYYY	Yes/ DDDMMYYYY
XXXXXX	XXXXXX	XXXXXX	No	YYYY	XX	XXXXXXXX	XXXXXX	Yes/ DDDMMYYYY	Yes/ DDDMMYYYY
XXXXXX	XXXXXX	XXXXX	Yes: XXXXXXXX	YYYY	XX	XXXXXX	XXXXXX	XXX	XXX

Abbreviation: PK = pharmacokinetic.
 [1] Age at Screening.

Programming Note: If subject has multiple races, concatenate them. If child-bearing potential is Yes, concatenate type of contraception with "." as shown in the shell.

Listing 16.2.4.1.2
Baseline Characteristics
All Subjects

Subject ID	Treatment Received	Height (cm)	Weight (kg)	BSA (%)	S-IGA [1]	B-IGA [1]	SI-NRS [2]	WI-NRS [2]
XXXXXX	XXXXXX	XX.X	XX.X	XX.X	X = XXXXX	X = XXXXX	XX	XX
XXXXXX	XXXXXX	XX.X	XX.X	XX.X	X = XXXXX *	X = XXXXX *	XX	XX
XXXXXX	XXXXXX	XX.X	XX.X	XX.X	X = XXXXX	X = XXXXX	XX	XX
XXXXXX	XXXXXX	XX.X	XX.X	XX.X	X = XXXXX	X = XXXXX	XX	XX
XXXXXX	XXXXXX	XX.X	XX.X	XX.X	X = XXXXX	X = XXXXX	XX	XX
XXXXXX	XXXXXX	XX.X	XX.X	XX.X	X = XXXXX	X = XXXXX	XX	XX

Abbreviations: B-IGA = body investigator global assessment; BSA = body surface area; S-IGA = scalp investigator global assessment; SI-NRS = Scalp Itch – Numeric Rating Scale; WI-NRS = Worst Itch – Numeric Rating Scale.

Note: Weight and % BSA affected by disease are the values at Screening. Height was collected at Baseline Day 0.

[1] For S-IGA and B-IGA, baseline is the last non-missing measurement taken before the first application of study drug. * = Screening visit was used as baseline.

[2] For SI-NRS and WI-NRS, baseline is the last non-missing measurement taken on or before the day of first application of study drug.

Programming Note: For S-IGA and B-IGA scores, if VISIT is not Baseline Day 0 for the record where ABLFL=Y, then add a * to the end of the concatenated numeric + text result, as shown in the shell.

Listing 16.2.4.2
 Medical History
 All Subjects

Subject ID	Treatment Received	Subject History of Psoriasis Involvement	Type of History	Other Medical History Conditions	
				System Organ Class/ Preferred Term/ Verbatim Term	Start Date (Study Day)/ End Date (Study Day)
XXXXXX	XXXXXX	Knees/Elbow: Yes/ Genitalia: No	Topical Corticosteroids: Yes/ Topical Vitamin D Derivatives: No	XXXXXXXXXXXXXXXXXX XXXXXXXXXXXXXXXXXX XXXXXXXXXXXXXXXXXX	DDMMYYYY (X) DDMMYYYY (X)
			XXXXXXXXXXXXXXXXXX XXXXXXXXXXXXXXXXXX XXXXXXXXXXXXXXXXXX	DDMMYYYY (X) DDMMYYYY (X)	
			XXXXXXXXXXXXXXXXXX XXXXXXXXXXXXXXXXXX XXXXXXXXXXXXXXXXXX	DDMMYYYY (X) DDMMYYYY (X)	
			XXXXXXXXXXXXXXXXXX XXXXXXXXXXXXXXXXXX XXXXXXXXXXXXXXXXXX	DDMMYYYY (X) DDMMYYYY (X)	
XXXXXX	XXXXXX	Knees/Elbow: Yes/ Genitalia: No	Topical Corticosteroids: Yes/ Topical Vitamin D Derivatives: No	XXXXXXXXXXXXXXXXXX XXXXXXXXXXXXXXXXXX XXXXXXXXXXXXXXXXXX	DDMMYYYY (X) Ongoing
			XXXXXXXXXXXXXXXXXX XXXXXXXXXXXXXXXXXX XXXXXXXXXXXXXXXXXX	DDMMYYYY (X) Ongoing	

Abbreviation: MedDRA = Medical Dictionary for Regulatory Activities.

Note: Study day is calculated relative to the date of first application of study drug. Medical history was coded using MedDRA version 23.0. Only subjects with medical history recorded are listed.

Programming note: SOC & PT text should be presented as is from the dataset.

Listing 16.2.5.1
Study Drug Application at the Study Site
All Subjects

Subject ID	Treatment Received	Was Study Drug Application Performed at Study Site?	Study Visit	Date/Time of Application (Study Day)	Pre-Application Can Weight (g) Measurement	Post-Application Can Weight (g) Measurement	Applied Dose (g)	Reason Pre- and/or Post-Application Can Weight Measurement not Performed	Kit Number/ Can ID
XXXX	XXXXXX	Yes	XXXXXX	DDMMYYYY/HH:MM (X)	XX	XX	XX		XXXX/ XX
			XXXXXX	DDMMYYYY/HH:MM (XX)	XX.X	XX.X	XX.X		XXXX/ XX
			XXXXXX	DDMMYYYY/HH:MM (XX)	XX	XX	XX		XXXX/ XX
		No: XXXXXX	XXXXXX						XXXX/ XX
XXXX	XXXXXX	Yes	XXXXXX	DDMMYYYY/HH:MM (X)	XX	XX	XX		XXXX/ XX
			XXXXXX	DDMMYYYY/HH:MM (XX)	XX	XX	XX.X		XXXX/ XX
			XXXXXX	DDMMYYYY/HH:MM (XX)	XX	Not Done		XXXXXXXXXXXXXXXXXX	XXXX/ XX

Note: Study day is calculated relative to the date of first application of study drug.

Programming note: For Pre & Post-Application Can Weight Measurement columns, if the weight measurement is not performed, set the value to be "Not Done". If drug not administered, concatenate reason (COVID-19 Disruption or other specify text) as shown in shell.

Listing 16.2.5.2
 Cans
 All Subjects

Subject ID	Treatment Received	Kit Number/ Can ID	Can Dispensed? Reason if No	Date Dispensed (Study Day)	Dispense Weight (g)	Can Returned? Reason if No	Date Returned (Study Day)	Return Weight (g)
XXXXX	XXXXXX	XXXXX/ XX	Yes	DDMMYYYY (X)	XX.X	Yes	DDMMYYYY (X)	XX.X
		XXXXX/ XX	Yes	DDMMYYYY (X)	XX.X	Yes	DDMMYYYY (X)	XX.X
		XXXXX/ XX	Yes	DDMMYYYY (X)	ND	Yes	DDMMYYYY (X)	ND
XXXXX	XXXXXX	XXXXX	No: XXXXX			No: XXXXX		

Abbreviation: ND = not done.

Note: Study day is calculated relative to the date of first application of study drug.

Programming note: within subject, sort by dispense date, return date, kit number and CAN ID.

Listing 16.2.5.3
 Diary Dispensation
 All Subjects

Subject ID	Treatment Received	Diary Dispensation Visit	Diary Dispensed?	Date Dispensed (Study Day)	Diary Returned Visit	Diary Returned and Reviewed?	Reason Diary not Returned	Date Returned (Study Day)
XXXXX	XXXXXX	XXXXXX	Yes	DDMMYYYY (X)	XXXXXX	Yes		DDMMYYYY (X)
		XXXXXX	Yes	DDMMYYYY (X)	XXXXXX	Yes		DDMMYYYY (X)
		XXXXXX	Yes	DDMMYYYY (X)	XXXXXX	No	XXXXXXXXXXXX	
XXXXX	XXXXXX	XXXXXX	No		XXXXXX	No	XXXXXXXXXXXX	

Note: Study day is calculated relative to the date of first application of study drug.

Listing 16.2.5.4
Compliance (CRF)
All Subjects

Subject ID	Treatment Received	Study Visit	Subject Compliant with Medication?	Date of Compliance Check (Study Day)	Compliance [1]	Overall Compliance [2]	Was Subject Retrained if not Compliant with Medication
XXXXXX	XXXXXX	XXXXXX XXXXXX XXXXXX	XXX XXX XXX	DDMMYYYY (X) DDMMYYYY (X) DDMMYYYY (X)	XX.X % XX.X % XX.X %	XX.X %	
XXXXXX	XXXXXX	XXXXXX XXXXXX XXXXXX	XXX XXX XX	DDMMYYYY (X) DDMMYYYY (X) DDMMYYYY (X)	XX.X % XX.X %	XX.X%	XXX

Abbreviations: IP = investigational product; CRF = case report form.

Note: Study day is calculated relative to the date of first application of study drug.

[1] This data comes from CRF page, unless otherwise specified.

[2] Overall compliance was calculated based on number of applications divided by the expected number of IP applications for each subject. Number of expected IP applications was calculated as number of days between first and last application of IP (last treatment date - first treatment date + 1). Number of IP applications was calculated as number of expected IP applications - missed IP applications as collected in the CRF.

Programming note: Populate overall compliance only for the first visit.

Listing 16.2.5.5
 Missed Doses
 All Subjects

Subject ID	Treatment Received	Study Visit	Date of Missed Dose (Study Day)	Missed Dose due to COVID-19 Disruption?	Reason for Missed Dose
XXXXXX	XXXXXX	XXXXXX XXXXXX	DDMMYYYY (X) DDMMYYYY (X)	No No	XXXXXXXXXXXXXXXXXX XXXXXXXXXXXXXXXXXX
XXXXXX	XXXXXX	XXXXXX	DDMMYYYY (X)	Yes	XXXXXXXXXXXXXXXXXX
XXXXXX	XXXXXX	XXXXXX XXXXXX	DDMMYYYY (X) DDMMYYYY (X)	No No	XXXXXXXXXXXXXXXXXX XXXXXXXXXXXXXXXXXX

Abbreviation: COVID-19 = novel coronavirus disease-19.

Note: Study day is calculated relative to the date of first application of study drug.

Programming note: Only subjects with missed doses should be presented in this listing.

Listing 16.2.5.6
 Pharmacokinetic Blood Collection
 All Consenting Subjects with Pharmacokinetic Data Collected

Subject ID	Treatment Received	PK Sample Collected at this Visit? Reason if No	Study Visit	PK Sample Collected Pre-Dose	PK Collection Time Point	Date/Time of Assessment (Study Day)	Accession Number	BSA Treated at the Time of PK Sample Collection	Roflumilast Concentration (unit)
XXXXXX	XXXXXX	XXX	XXXXXX	XXX	XXXXX	DDMMYY/ HH:MM (X)	XXXXX	XX.X %	XX.X
			XXXXXX	XXX	XXXXX	DDMMYY/ HH:MM (X)	XXXXX	XX %	XX.X
			XXXXXX	XXX	XXXXX	DDMMYY/ HH:MM (X)	XXXXX	XX %	XX.X
		No: XXXXXXXX	XXXXXX	XX	XXXXX	DDMMYY/ HH:MM (X)			

Abbreviation: BLQ = Below the limit of quantification; BSA = body surface area; PK = pharmacokinetic.
 Note: Study day is calculated relative to the date of first application of study drug.

Listing 16.2.5.7
 Pharmacokinetic Calculated Parameters
 PK Population

Subject ID	Treatment Received	Study Visit	AUC _{0-t} (unit)	AUC _{0-∞} (unit)	T _{max} (unit)	T _{lag} (unit)	T _{last} (unit)	C _{max} (unit)	C _{min} (unit)
XXXXX	XXXXXXX	XXXXXX	XX	XX	XX	XX	XX	XX	XX
		XXXXXX	XX	XX	XX	XX	XX	XX	XX
		XXXXXX	XX	XX	XX	XX	XX	XX	XX
		XXXXXX	XX	XX	XX	XX	XX	XX	XX

Abbreviation: PK = pharmacokinetic.

Programming note: The above parameters are expected. However the final parameters provided by the pharmacokineticist will be listed and may be different than shown.

Listing 16.2.6.1
Scalp Investigator Global Assessment (S-IGA)
All Subjects

Subject ID	Randomized Treatment	Was Assessment Completed? Reason if No	If Yes, Telemedicine or Delay in Assessment Collection [1]	Study Visit	Date/Time of Assessment (Study Day)	Result	Text Result	Change from Baseline	S-IGA Success [2]
XXXXXX	XXXXXX	Yes	No	XXXXXXX	DDMMYYYY/hh:mm (X)	X	XXXXXXXXXXXX		
		Yes	Yes: Delay in Assessment Collection	XXXXXXX	DDMMYYYY/hh:mm (X)	X	XXXXXXXXXXXX	X	Yes
		No: COVID-19 Disruption		XXXXXXX					
		Yes	No	XXXXXXX	DDMMYYYY/hh:mm (X)	X	XXXXXXXXXXXX	X	Yes
XXXXXX	XXXXXX	Yes	Yes: Assessment Completed via Telemedicine	XXXXXXX	DDMMYYYY/hh:mm (X)	X	XXXXXXXXXXXX		
		No: XXXXXXXXX		XXXXXXX	DDMMYYYY/hh:mm (X)				

Abbreviations: COVID-19 = novel coronavirus disease-19; S-IGA = scalp investigator global assessment.

Note: Study day is calculated relative to the date of first application of study drug. Baseline is the last non-missing measurement taken before the first application of study drug. Change from baseline is calculated as Result – Baseline.

[1] Due to COVID-19 disruption.

[2] S-IGA Success (“Yes”) is defined as an S-IGA score of “Clear” or “Almost Clear” plus a ≥2-grade improvement from baseline at Weeks 2, 4, 8, and 9; “No” otherwise.

Programming note: Concatenate reason not done (COVID-19 Disruption or other specify text) as shown in the shell. For the “if Yes, Telemedicine or Delay in Assessment Collection” column, do the following: if the answer to both questions (was assessment completed via telemedicine or was delayed) is No, display “No”; if the answer to only was assessment completed via telemedicine is yes, set to “Yes: Assessment Completed via Telemedicine”; if the answer to only did COVID-19 disruption cause/contribute to delay, set to “Yes: Delay in Assessment Collection”; if both are yes, set to “Yes: Assessment Completed via Telemedicine: Delay in Assessment Collection”.

Listing 16.2.6.2
Body Investigator Global Assessment (B-IGA)
All Subjects

Programming note: Same as shell 16.2.6.1. Update any instances of S-IGA to B-IGA.

Listing 16.2.6.3
Psoriasis Scalp Severity Index (PSSI)
All Subjects

Subject ID	Randomized Treatment	Was Assessment Completed? Reason if No	If Yes, Telemedicine or Delay in Assessment Collection [1]	Study Visit	Date/Time of Assessment (Study Day)	Test	Numeric Result	Text Result	Change from Baseline	PSSI-50 [3]/ PSSI-75 [4]/ PSSI-90 [5]
XXXXXX	XXXXXX	Yes	No	XXXX	DDMMYYYY/hh:mm (X)	Erythema	2	XXXX		
						Induration	2	XXXXX		
						Desquamation	2	XXXX		
						Sum of Severity	6			
						Rating	2			
						Extent of Scalp Affected	2			
						PSSI Total Score [3]	12			
		Yes	Yes: Delay in Assessment Collection	XXXX	DDMMYYYY/hh:mm (X)	Erythema	2	XXXXX	XX	
						Induration	3	XXXXX	XX	
						Desquamation	2	XXXX	XX	
						Sum of Severity	7		XX	
						Rating	2		XX	
						Extent of Scalp Affected	2		XX	
						PSSI Total Score [2]	14		XX	XX/XX/XX

Abbreviations: COVID-19 = novel coronavirus disease-19; PSSI = Psoriasis Scalp Severity Index.

Note: Study day is calculated relative to the date of first application of study drug. Baseline is the last non-missing measurement taken before the first application of study drug. Change from baseline is calculated as Result – Baseline.

[1] Due to COVID-19 disruption.

[2] PSSI total score is calculated as (erythema score + induration + desquamation) × extent of scalp affected. The score ranges from 0 to 72. Erythema, induration, and desquamation are scored on a scale of 0 to 4, where 0 = absent and 4 = severest possible; extent of scale affected is scored on a scale of 0 to 6, where 0 = 0% of involved area and 6 = 90-100% of involved area.

[3] PSSI-50 is populated with "Yes" when there is an achievement of a 50% reduction in PSSI total score from baseline.

[4] PSSI-75 is populated with "Yes" when there is an achievement of a 75% reduction in PSSI total score from baseline.

[5] PSSI-90 is populated with "Yes" when there is an achievement of a 90% reduction in PSSI total score from baseline.

Programming note: Concatenate reason not done (COVID-19 Disruption or other specify text) as shown in the shell for Listing 16.2.6.1. For the "if Yes, Telemedicine or Delay in Assessment Collection" column, do the following: if the answer to both questions (was assessment completed via telemedicine or was delayed) is No, display "No"; if the answer to only was assessment completed via telemedicine is yes, set to "Yes: Assessment Completed via Telemedicine"; if the answer to only did COVID-19 disruption cause/contribute to delay, set to "Yes: Delay in Assessment Collection"; if both are yes, set to "Yes: Assessment Completed via Telemedicine; Delay in Assessment Collection". Only populate PSSI-50, PSSI-75, and PSSI-90 on PSSI Total Score row.

Listing 16.2.6.4
Scalp Itch – Numeric Rating Scale (SI-NRS)
All Subjects

Subject ID	Randomized Treatment	Was Assessment Completed? Reason if No	If Yes, Telemedicine or Delay in Assessment Collection [1]	Study Visit	Date/Time of Assessment (Study Day)	Result	Change from Baseline	SI-NRS Success (baseline ≥ 4) [2]
XXXXXX	XXXXXX	Yes	No	XXXXXX	DDMMYYYY/hh:mm (X)	9		
		Yes	No	XXXXXX	DDMMYYYY/hh:mm (X)	X	X	Yes
		Yes	No	XXXXXX	DDMMYYYY/hh:mm (X)	X	X	Yes
		Yes	Yes: Delay in Assessment Collection	XXXXXX	DDMMYYYY/hh:mm (X)	X	X	Yes
XXXXXX	XXXXXX	Yes	No	XXXXXX	DDMMYYYY/hh:mm (X)	X	X	Yes
		No: XXXXXX	No	XXXXXX	DDMMYYYY/hh:mm (X)	X		

Abbreviations: COVID-19 = novel coronavirus disease-19; SI-NRS = Scalp Itch – Numeric Rating Scale.

